Appendix B Responsibilities of the Investigator

Clinical research studies sponsored by the sponsor are subject to ICH GCP and all the applicable local laws and regulations.

The investigator agrees to assume the following responsibilities:

1. Conduct the study in accordance with the protocol.
2. Personally conduct or supervise the staff who will assist in the protocol.
3. Ensure that study related procedures, including study specific (nonroutine/nonstandard panel) screening assessments are NOT performed on potential subjects, prior to the receipt of written approval from relevant governing bodies/authorities.
4. Ensure that all colleagues and employees assisting in the conduct of the study are informed of these obligations.
5. Secure prior approval of the study and any changes by an appropriate IRB/IEC that conform to ICH and local regulatory requirements.
6. Ensure that the IRB/IEC will be responsible for initial review, continuing review, and approval of the protocol. Promptly report to the IRB/IEC all changes in research activity and all anticipated risks to subjects. Make at least yearly reports on the progress of the study to the IRB/IEC, and issue a final report within 3 months of study completion.
7. Ensure that requirements for informed consent, as outlined in ICH and local regulations, are met.
8. Obtain valid informed consent from each subject who participates in the study, and document the date of consent in the subject's medical chart. Valid informed consent is the most current version approved by the IRB/IEC. Each informed consent form should contain a subject authorization section that describes the uses and disclosures of a subject's personal information (including personal health information) that will take place in connection with the study. If an informed consent form does not include such a subject authorization, then the investigator must obtain a separate subject authorization form from each subject or the subject's legally acceptable representative.
9. Prepare and maintain adequate case histories of all persons entered into the study, including eCRFs, hospital records, laboratory results, etc, and maintain these data for a minimum of 2 years following notification by the sponsor that all investigations have been discontinued or that the regulatory authority has approved the marketing application. The investigator should contact and receive written approval from the sponsor before disposing of any such documents.
10. Allow possible inspection and copying by the regulatory authority of GCP-specified essential documents.
11. Maintain current records of the receipt, administration, and disposition of sponsor-supplied drugs, and return all unused sponsor-supplied drugs to the sponsor.

12. Report adverse reactions to the sponsor promptly. In the event of an SAE, notify the sponsor within 24 hours.

Appendix C Elements of the Subject Informed Consent

In seeking informed consent, the following information shall be provided to each subject:

1. A statement that the study involves research.
2. An explanation of the purposes of the research.
3. The expected duration of the subject's participation.
4. A description of the procedures to be followed, including invasive procedures.
5. The identification of any procedures that are experimental.
6. The estimated number of subjects involved in the study.
7. A description of the subject's responsibilities.
8. A description of the conduct of the study.
9. A statement describing the treatment(s) and the probability for random assignment to each treatment.
10. A description of the possible side effects of the treatment that the subject may receive.
11. A description of any reasonably foreseeable risks or discomforts to the subject and, when applicable, to an embryo, fetus, or nursing infant.
12. A description of any benefits to the subject or to others that reasonably may be expected from the research. When there is no intended clinical benefit to the subject, the subject should be made aware of this.
13. Disclosures of appropriate alternative procedures or courses of treatment, if any, that might be advantageous to the subject and their important potential risks and benefits.
14. A statement describing the extent to which confidentiality of records identifying the subject will be maintained, and a note of the possibility that regulatory agencies, auditor(s), IRB/IEC, and the monitor may inspect the records. By signing a written informed consent form, the subject or the subject's legally acceptable representative is authorizing such access.
15. For research involving more than minimal risk, an explanation as to whether any compensation and an explanation as to whether any medical treatments are available if injury occurs and, if so, what they consist of or where further information may be obtained.
16. The anticipated prorated payment(s), if any, to the subject for participating in the study.
17. The anticipated expenses, if any, to the subject for participating in the study.
18. An explanation of whom to contact for answers to pertinent questions about the research (investigator), subject's rights, and IRB/IEC and whom to contact in the event of a research-related injury to the subject.
19. A statement that participation is voluntary, that refusal to participate will involve no penalty or loss of benefits to which the subject otherwise is entitled, and that the subject may discontinue

participation at any time without penalty or loss of benefits to which the subject is otherwise entitled.

20. The consequences of a subject's decision to withdraw from the research and procedures for orderly termination of participation by the subject.

21. A statement that the subject or the subject's legally acceptable representative will be informed in a timely manner if information becomes available that may be relevant to the subject's willingness to continue participation in the study.

22. A statement that results of pharmacogenomic analysis will not be disclosed to an individual, unless prevailing laws require the sponsor to do so.

23. The foreseeable circumstances or reasons under which the subject's participation in the study may be terminated.

24. A written subject authorization (either contained within the informed consent form or provided as a separate document) describing to the subject the contemplated and permissible uses and disclosures of the subject's personal information (including personal health information) for purposes of conducting the study. The subject authorization must contain the following statements regarding the uses and disclosures of the subject's personal information:

- a) that personal information (including personal health information) may be processed by or transferred to other parties in other countries for clinical research and safety reporting purposes, including, without limitation, to the following: (1) Takeda, its affiliates, and licensing partners; (2) business partners assisting Takeda, its affiliates, and licensing partners; (3) regulatory agencies and other health authorities; and (4) IRBs/IECs;
- b) it is possible that personal information (including personal health information) may be processed and transferred to countries that do not have data protection laws that offer subjects the same level of protection as the data protection laws within this country; however, Takeda will make every effort to keep your personal information confidential, and your name will not be disclosed outside the clinic unless required by law;
- c) that personal information (including personal health information) may be added to Takeda's research databases for purposes of developing a better understanding of the safety and effectiveness of the study medication(s), studying other therapies for patients, developing a better understanding of disease, and improving the efficiency of future clinical studies;
- d) that subjects agree not to restrict the use and disclosure of their personal information (including personal health information) upon withdrawal from the study to the extent that the restricted use or disclosure of such information may impact the scientific integrity of the research; and
- e) that the subject's identity will remain confidential in the event that study results are published.

25. Women of childbearing potential (eg, nonsterilized, premenopausal women) who are sexually active must use adequate contraception (as defined in the informed consent) from Screening and throughout the duration of the study, and for 30days weeks after last dose of study medication. Regular pregnancy tests will be performed throughout the study for all women of childbearing potential. If a subject is found to be pregnant during study, study medication will be discontinued and the investigator will offer the subject the choice to receive unblinded treatment information.
26. Men must use adequate contraception (as defined in the informed consent) from Screening and throughout the duration of the study. If the partner or wife of the subject is found to be pregnant during the study, the investigator will offer the subject the choice to receive unblinded treatment information.
27. A statement that clinical trial information from this trial will be publicly disclosed in a publicly accessible website, such as ClinicalTrials.gov.

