7.1 Inclusion Criteria

Subject eligibility is determined according to the following criteria prior to entry into the study:

1. In the opinion of the investigator, the subject is capable of understanding and complying with protocol requirements.
2. The subject or, when applicable, the subject's legally acceptable representative signs and dates a written, informed consent form and any required privacy authorization prior to the initiation of any study procedures including requesting that a subject fast for any laboratory evaluations.
3. The subject is a healthy adult man or woman of Chinese descent.
4. The subject is aged 18 to 45 years, inclusive, at the time of informed consent and study medication dose.
5. The subject weighs at least 50 kg and has a body mass index (BMI) from 19.0 to 26.0 kg/m², inclusive at Screening Visit.
6. A man who is nonsterilized* and sexually active with a woman of childbearing potential* agrees to use adequate contraception* from signing of informed consent throughout the duration of the study and for 30 days after last dose of study drug.
7. If a woman of childbearing potential* is sexually active with a nonsterilized* man, she agrees to routinely use adequate contraception* from signing of informed consent throughout the duration of the study and for 30 days following the last dose of study drug. Women of childbearing potential* must have a negative pregnancy test at Screening and Check-in (Day -1 of Period 1) and they must not be nursing.

*Definitions and acceptable methods of contraception are defined in Section [9.1.9](#) Contraception and Pregnancy Avoidance Procedure and reporting responsibilities are defined in Section [9.1.10](#) Pregnancy.

8. Subject has clinical chemistry, hematology, and complete urinalysis (fasted for at least 8 hours) at the Screening Visit and Check-in (Day -1) results within the reference range for the testing laboratory unless the out of range results are deemed not clinically significant by both the investigator and Medical Monitor.

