9.1.9 Contraception and Pregnancy Avoidance Procedure

From signing of informed consent, throughout the duration of the study, and for 30 days after last dose of study medication, nonsterilized** men who are sexually active with a woman of childbearing potential* must use barrier contraception (eg, condom with spermicidal cream or jelly). In addition, they must be advised not to donate sperm during this period.

From signing of informed consent, throughout the duration of the study, and for 30 days after last dose of study medication, female subjects of childbearing potential* who are sexually active with a nonsterilized male partner** must use adequate contraception. In addition they must be advised not to donate ova during this period.

*Women NOT of childbearing potential are defined as those who have been surgically sterilized (hysterectomy, bilateral oophorectomy or tubal ligation) or who are postmenopausal (defined as continuous amenorrhea of at least 1 year and FSH >40 IU/L or at least 5 years since last regular menses, confirmed before any study medication is implemented, confirmed before any study medication is administered). Subject without bilateral tubal ligation documentation must follow one of the other methods of contraception as described below.

**Sterilized men should be at least 1 year postvasectomy and have confirmed that they have obtained documentation of the absence of sperm in the ejaculate.

An acceptable method of contraception is defined as one that has no higher than a 1% failure rate. In this study, where medications and devices containing hormones are included (provided the subject has been on a stable dose for a minimum of 90 days prior to Day 1), the only acceptable methods of contraception are:

Barrier methods (each time the subject has intercourse):

- Cap (plus spermicidal cream or jelly) PLUS male condom and spermicide.
- Diaphragm (plus spermicidal cream or jelly) PLUS male condom and spermicide.

Intrauterine devices (IUDs):

- Copper T PLUS condom or spermicide.
- Progesterone T PLUS condom or spermicide.

Hormonal contraceptives:

- Implants.
- Hormone shot/injection.
- Combined pill.
- Minipill.
- Patch.
- Vaginal ring PLUS male condom and spermicide.

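### The consent element for men (Appendix C, item 26) ends contraception with the study, while inclusion criterion 6 and Section 9.1.9 carry it to 30 days after the last dose

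*Protocol*

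**What the plan says.** Three places in the protocol set a contraception period for male subjects.

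- **Section 7.1, inclusion criterion 6.** A nonsterilized man who is sexually active with a woman of childbearing potential must agree to contraception from consent, "throughout the duration of the study and for 30 days after last dose of study drug".
- **Section 9.1.9.** The same period is imposed directly: "throughout the duration of the study, and for 30 days after last dose of study medication, nonsterilized men" in that situation must use barrier contraception.
- **Appendix C, item 26.** "Men must use adequate contraception (as defined in the informed consent) from Screening and throughout the duration of the study". The sentence stops there.

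Section 9.1.10 also has partner pregnancies recorded during the study and for up to 30 days after the last dose.

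For women, criterion 7 says "throughout the duration of the study and for 30 days following the last dose of study drug" and Section 9.1.9 agrees: "for 30 days after last dose of study medication, female subjects of childbearing potential". Appendix C, item 25 has a post-dose clause too, but its unit is garbled: "for 30days weeks after last dose of study medication".

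**The concern.** Appendix C is the list from which a consent form is built. Section 15.0 points to the appendices for the consent requirements, and Section 15.2 makes the investigator responsible for preparing the form. Section 9.1.9 has subjects sign to say they understand the pregnancy-avoidance requirements.

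A form that follows item 26 as written would have men sign for a period ending with the study, although criterion 6 admits them only if they agree to a longer one. A man relying on such a form could stop contraception while the eligibility commitment, and the window in which a partner pregnancy is to be recorded, are still running. What is at stake is the information given to participants about pregnancy risk.

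**Working it through.** The plan gives no figure of its own to reproduce. The check is a comparison of passages and a count of days.

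**Step 1: compare the stated periods for men.**

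| Source | Start | End |
|---|---|---|
| Inclusion criterion 6 | signing of consent | 30 days after last dose |
| Section 9.1.9 | signing of consent | 30 days after last dose |
| Appendix C, item 26 | Screening | end of study |

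Consent is obtained at Screening (protocol Appendix A), so the starting points amount to the same thing. Only the end differs.

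**Step 2: does anything in item 26 supply the missing period?** No. Its parenthesis, which defers to the consent form, qualifies what counts as adequate contraception and not how long it lasts. Item 25, directly above it, does carry a post-dose clause, so the format of the list does not explain the omission.

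**Step 3: is this superseded text?** No. Appendix C is part of the current protocol, and the Amendment 03 change list (Section 1.3 and Appendix F) names changes only to Appendix E, Sections 9.1.8 and 9.1.12, and Section 9.4.

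**Step 4: size of the gap.** There is a single dose on Day 1, so

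gap = 30 days − (days from dose to end of study).

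Item 26 does not say when the study ends, and the protocol supports two readings.

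- *Follow-up contact 5 to 10 days after dosing* (Figure 6.a, Section 10.2.1.1): 30 − 10 = 20 days, and 30 − 5 = 25 days.
- *Discharge from the study on Day 2* (Appendix A, footnote c), which is 1 day after dosing: 30 − 1 = 29 days.

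The range is therefore about 20 to 29 days.

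**Step 5: who is affected.** Forty subjects are planned, and Section 6.2 promises only an effort to enrol equal numbers of men and women. On that plan there would be about 40 ÷ 2 = 20 men. The gap applies to those among them who are nonsterilized and sexually active with a woman of childbearing potential, a number the documents do not give.

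**Step 6: the item for women.** Criterion 7 and Section 9.1.9 both give 30 days. Exclusion criterion 12 also uses 30 days, counted from participation. None of these passages counts in weeks. Item 25 contains the 30-day figure with a stray second unit after it.

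**The case against.** The strongest reply is that Appendix C is a list of elements and not the consent form. The form itself is not among the documents and may already state 30 days. It must be approved by the ethics committee and the sponsor (Section 15.2). Criterion 6 and Section 9.1.9 bind the site whatever item 26 says, and a man cannot be enrolled under criterion 6 without agreeing to the 30 days. Items 25 and 26 also look like template text that was not fully adapted, since both offer unblinded treatment information in an open-label study. All of this stands. It lowers the chance that any participant was misinformed, but it does not remove the discrepancy in item 26.

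Three stronger readings are tempting, and the documents do not support them.

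- **That men are given no contraception period after dosing at all.** Item 26 runs through the study, which includes the time from dosing to study end. What is missing is any period beyond that.
- **That women face a contradiction of 30 days against 30 weeks.** Thirty weeks would be 30 × 7 = 210 days, 180 days longer than the other sections state. But item 25 itself contains the 30-day figure, and the other passages on women use days. This is most simply read as an editing slip, so the 180-day difference should not be counted.
- **That men were in fact told a shorter period.** Without the consent form this cannot be known.

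**Conclusion.** The point holds for men as an inconsistency within the protocol. Item 26 ends the requirement with the study, while criterion 6 and Section 9.1.9 carry it to 30 days after the last dose, the same limit that Section 9.1.10 uses for recording partner pregnancies.

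The shortfall is 20 to 25 days if the study is taken to end at the follow-up contact, and about 29 days if it ends at Day 2 discharge. The choice between those endpoints is an assumption, because item 26 does not define study end. For women, all that remains is a clerical correction in item 25.

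The matter bears on what participants are told. It does not touch the pharmacokinetic endpoints, the analysis sets or the sample size. No view is taken here on which contraception period is clinically right.

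**What to change.** Reconcile Appendix C, item 26 with inclusion criterion 6 and Section 9.1.9, so that a single period, with the same starting and ending events, appears in all three. Then compare the approved consent form with the reconciled text, and correct the form through the ethics committee if it differs. In the same edit, remove the duplicated unit in item 25 so that it agrees with criterion 7 and Section 9.1.9.

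The cost is two wording corrections in one appendix and one check of the consent form. No procedure, visit or analysis needs to change.

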Appendix D Investigator Consent to Use of Personal Information

Takeda will collect and retain personal information of investigator, including his or her name, address, and other personally identifiable information. In addition, investigator's personal information may be transferred to other parties located in countries throughout the world (eg, the United Kingdom, United States, and Japan), including the following:

- Takeda, its affiliates, and licensing partners.
- Business partners assisting Takeda, its affiliates, and licensing partners.
- Regulatory agencies and other health authorities.
- IRBs and IECs.

Investigator's personal information may be retained, processed, and transferred by Takeda and these other parties for research purposes including the following:

- Assessment of the suitability of investigator for the study and/or other clinical studies.
- Management, monitoring, inspection, and audit of the study.
- Analysis, review, and verification of the study results.
- Safety reporting and pharmacovigilance relating to the study.
- Preparation and submission of regulatory filings, correspondence, and communications to regulatory agencies relating to the study.
- Preparation and submission of regulatory filings, correspondence, and communications to regulatory agencies relating to other medications used in other clinical studies that may contain the same chemical compound present in the study medication.
- Inspections and investigations by regulatory authorities relating to the study.
- Self-inspection and internal audit within Takeda, its affiliates, and licensing partners.
- Archiving and audit of study records.
- Posting investigator site contact information, study details and results on publicly accessible clinical trial registries, databases, and websites.

Investigator's personal information may be transferred to other countries that do not have data protection laws that offer the same level of protection as data protection laws in investigator's own country.

Investigator acknowledges and consents to the use of his or her personal information by Takeda and other parties for the purposes described above.

Appendix E Collection, Storage, and Shipment of Bioanalytical Samples

Instructions for Processing of Plasma Samples for Pharmacokinetic Analysis

1. Collect 6 mL of venous blood into a chilled Becton-Dickinson Vacutainer. For all TAK-390MR samples, blood samples should be collected into vacutainers containing anticoagulant K₂EDTA.
2. Gently invert the vacutainer several times to mix the additive with the collected blood prior to centrifugation and place immediately on ice or keep at ambient temperature.
3. Centrifuge the vacutainers for 10 minutes at approximately 1200 relative centrifugal force (RCF) at approximately 4°C in a refrigerated centrifuge or at ambient temperature. Note: if using a collection device other than Becton-Dickinson, refer to manufacturer's instruction for proper centrifugation force and time.
4. Immediately following centrifugation, gently remove plasma from the packed cells. Split the plasma evenly between the 2 aliquots. A minimum of approximately 1.2 mL needs to be obtained for each sample. Labeling may include protocol number (TAK-390MR_106), matrix (ie, plasma), analyte (TAK-390MR), enrollment number, nominal day and time, and either "SET 1" (for original sample) or "SET 2" (for duplicate sample).
5. Cap the labeled storage tubes and freeze the plasma samples immediately at approximately -20°C or lower. No more than 120 minutes will elapse between blood collection and freezing the plasma sample.
6. Keep samples frozen at approximately -20°C or lower until shipment site. SET 1 samples will be shipped first on dry ice, followed by shipment of duplicate SET 2 samples after SET 1 samples have been received by the analytical laboratory.

Shipping of Plasma Samples

Site may adhere to the site's SOPs on shipping samples if the SOP differs from the sample instructions provided.

Biological samples should be shipped on sufficient dry ice to prevent thawing during transit. Samples should be shipped to arrive at their destination during normal business hours (local time). It is recommended that samples be shipped on Monday, Tuesday or Wednesday and 2 days before a national holiday, in order to minimize the possibility of samples arriving at their destination on a weekend or holiday. For shipments outside these periods, it is recommended that a premium carrier who will replenish dry ice during shipment as necessary be used. Other shipping arrangements may be allowed with the agreement of the Sponsor. If duplicate samples are to be shipped, send SET 1 samples and await confirmation of arrival before shipping the duplicate SET 2 samples.

Before shipping, make sure the sample tubes are tightly sealed. Separate each subject's samples as follows:

1. Separate the duplicate SET 2 samples from the SET 1 samples.

2. Place SET 1 samples for each subject into zipper lock bag containing additional absorbent material.
3. Using a permanent marker, write the enrollment number, sample matrix (ie, plasma or urine), analyte (TAK-390MR), number of samples, and “SET 1” on each zipper lock bag.
4. Place the bags of individual subject’s samples into a larger plastic bag so that samples are double bagged. Duplicate SET 2 samples should be returned to the freezer for storage.
5. An inventory of individual samples should accompany each shipment and should include the Sponsor’s name (Takeda), study drug (TAK-390MR), protocol number (TAK-390MR_106), investigator’s name, sample type (ie, plasma), subject’s enrollment number, nominal collection day and time, and intended sample storage conditions. When duplicate SET 2 samples are being shipped, make a copy of the original SET 1 sample inventory and mark as “SET 2.” Place the inventory paperwork into a large zipper lock bag. SET 1 samples will be shipped first on dry ice, followed by shipment of duplicate SET 2 samples after SET 1 samples have been received by the analytical laboratory.
6. For sample packing, use dry ice generously (eg, 20-25 pounds per day of transit) to safeguard against longer than expected shipping times and delays. Use newspaper or other material to insulate the double-bagged samples from direct contact with the dry ice. Place the sample bundles into a Styrofoam container (or other suitable container) and fill the excess space with dry ice slabs or ice pellets (preferably the latter). Make a note of the estimated weight of the dry ice used per shipping container.
7. Place the inventory paperwork (in a large self-sealing bag) on top of the dry ice in the Styrofoam container. Place the lid on the Styrofoam container and seal completely with strapping tape. Place the Styrofoam container in a cardboard shipping carton and seal securely with strapping tape.
8. Mark the outside of shipping carton(s) with a tally number (eg, 1 of 5, 2 of 5).
9. Affix an address label to each shipping carton. Complete the address label with the following information:
Plasma Samples for TAK-390MR_106
Personally Protected Data
10. Affix a carbon dioxide label on each carton, specifically:
Carbon Dioxide Solid UN-1845
Class 9 PKG GR III
Quantity _____
(fill in weight to nearest lb/kg and specify unit of measure used)

11. Affix 2 dry ice symbol labels on opposite sides of the carton. Mark **KEEP FROZEN** on each carton. Specify a return address and contact person on the carton.
12. Obtain the airway bill number and a receipt of shipment from the carrier.
13. After shipping of the samples, **contact the analytical site and CRO representative** to notify them of next day delivery. When calling, provide the following information:

Name of courier or transport company
Time and date the shipment left the clinical site
Airway bill number

Instructions for processing and shipping of blood samples for genotyping analysis

Detailed instructions for the handling and shipping of samples will be provided in the Lab Manual.

